- In-hospital mortality, truncated at 90 days.

The protocol did not call for systematic measurement of intra-abdominal pressure.

Therefore, intra-abdominal pressure was measured according to physicians' discretion when they suspected of intra-abdominal hypertension.

Analysis methods

Continuous distribution will be assessed by visual inspection of histograms and D'Agostino-Pearson's normality tests. Variables will be expressed as counts and percentages, mean and standard deviation (SD), or median and interquartile range (IQR), whenever appropriate, as indicated in mock tables 1 to 3, which we intend to include in the main results paper.

The evolution of hemodynamic and perfusion variables in both groups during the study will be presented as in mock table 2. We will carry out linear mixed models for continuous variables where Gaussian error distribution applies to account for the repeated measurements on the same patient. Binary variables will be tested using logistic mixed regression models and continuous variables with non-symmetrical distributions such as Lactate and Mottling score will use the distribution that best fit the data.

We will assess the effect of PPTR versus LTR on the primary outcome using Cox proportional hazards models, with adjustment for 5 pre-specified baseline covariates: APACHE II score, SOFA score, lactate level, CRT and source of infection, as fixed

(individual-level) effects. Results will be reported as hazard ratios with 95% confidence intervals (CI) and P-values. We should also present Kaplan Meier curves.

Effects on secondary and tertiary outcomes will be presented as hazard ratio for 90-day all-cause mortality and renal replacement therapy within 28 days, or risk difference for all other binary outcomes, along with 95% CI and P-values (calculated with Fisher's exact tests), as shown in mock table 3. The effect on 90-day all-cause mortality and the need of renal replacement therapy within 28 days will be assessed with Cox-proportional hazard model without adjustment for baseline covariates.

We will estimate the effect on mechanical ventilation-free days, renal replacement therapy-free days and vasopressors-free days within 28 days with generalized linear models using the distribution that better fits the data (possibly truncated Poisson distribution). Effects on organ dysfunction at 72 hours (measured by SOFA) will be calculated with generalized linear models with the distribution that better fits the data with adjustment for the baseline SOFA. Effect on other continuous outcomes, such as ICU or hospital length of stay, amount or resuscitation fluids, fluid balance, will also be calculated with generalized linear models with the distribution that better fits the data (normal, gamma, inverse Gaussian, or other), without adjustment for covariates.

Subgroup analyses

We will use Cox proportional hazards adjusted for baseline covariates (same as main analysis) to assess interactions between treatment effect and the following prespecified subgroups: a) Patients with lactate > 4.0 mmol/L versus equal or lower than 4 mmol/L; b) Patients without a confirmed source of infection (as this could increase the translation of

the study to other critically ill) versus those with confirmed source of infection; c) Patients with APACHE II lower versus equal or higher than 25; d) Patients with SOFA score lower versus equal or higher than 10; e) Patients with a more than 10% difference in lactate levels between the very first one measured and the baseline when starting the study.

Sensitivity analysis

We will assess the effect of PPTR compared to LTR on 28-day mortality using a frailty Cox model with site as random effect and adjustment for the same baseline co-variables as in the main analysis (APACHE II score, SOFA score, lactate level, CRT and source of infection).

Harms

Our primary, secondary and tertiary outcomes are intended to reflect potential harms resulting from the PPTR versus LTR approach for managing septic shocks.

Missing data

Primary outcome (28-day mortality) will be treated as time to event outcome and reported as Cox proportional hazard models, patients with loss of follow up will be censored in the last contact. We will use multiple imputation methods to assess treatment effect on the primary outcome if there are cases without no follow-up information at all. As a sensitivity analysis, we will also assess the effect on the primary outcome using complete case data.

Statistical software

Analyses will be performed using the R (R Core Team, 2017, Vienna, Austria) software.

CONCLUSION

According to the best trial practice, we report our statistical analysis plan and data

management plan prior to locking the database and starting analyses. We anticipate that this document will prevent analysis bias and enhance the utility of the reported results.

Competing interests The authors declare that they have no competing interests.

Funding The study is financed in part by an internal grant from the Departamento de Medicina Intensiva, Facultad de Medicina, Pontificia Universidad Católica de Chile.

Authors' contributions GH, ABC, and JB are guarantors of the entire manuscript; JB, JLT, GH, GOT, AD, GF, MC, FJH, ABC, RC, LA, LD designed the study; All the authors will help in the data interpretation and the final manuscript draft. All authors read and approved this final manuscript.

Acknowledgements.

We acknowledge the support from the Departamento de Medicina Intensiva, Facultad de Medicina, Pontificia Universidad Católica de Chile.

ANDROMEDA–SHOCK Investigators consists of:

Writing and Steering Committee: [name] (chair), [name], [name], [name], [name], [name], [name], [name], [name], [name], [name], [name] (co-chair)

References

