The protocol can be stopped at any moment for safety considerations during the 8-h study period if the attending intensivist considers that the patient has developed unexpected and severe complications or evolves into refractory shock, conditions that under his judgment require liberalization of management. This action has to be reported on the case report form (CRF), and the patient will be followed up with major outcomes, and included in the intention-to-treat (ITT) analysis. Specific safety measures for fluid administration, vasopressor test and inodilator use are specified above.

Suspected unexpected serious adverse reactions (SUSAR)

Any adverse event that occurs in a clinical trial subject, which is assessed by the study investigator as being unexpected, serious and as having a reasonable possibility of a causal relationship with the study procedure will be reported. Reports of these reactions are subject to expedited submission to health authorities. SUSAR's will be analyzed by both the SCC and the data safety monitoring committee (DSMC).

Blinding

Since the intervention will be administered to critically ill patients (mostly sedated), blinding of these patients is not necessary. Because this is a non-pharmacological intervention, blinding of the medical team is not feasible.

Data collection and management

Study follow-up and the variables that will be collected are described below.

Baseline

Demographics, comorbidities, acute physiology and chronic health evaluation (APACHE) II [31], sepsis source and treatment

pre-ICU resuscitation and fluid balance

Sequential Organ Failure Assessment (SOFA) [26] + and Acute Kidney Injury Network (AKI) criteria [32]

Hemodynamics: HR, SBP, diastolic blood pressure (DBP), MAP, CVP, FR status, intraabdominal pressure (IAP), NE levels, diuresis.

Perfusion: lactate, central venous O₂ saturation (ScvO₂), central venous arterial pCO₂ gradient (P(cv-a)CO₂), Hb, central venous and arterial blood gases, CRT, mottling score.

Evolution

SOFA and AKI criteria at 8, 24, 48 and 72 h

Hemodynamics hourly up to 8 h

Fluid administration and balance at 8, 24, 48 and 72 h

Complete perfusion assessment when the targeted parameter is normalized and then at 8, 24, 48 and 72 h

Register of vasoactive drugs and dobutamine/milrinone use

Register of MV and RRT

Source control re-analysis at 4 h

Rescue therapies: HVHF, vasopressin, epinephrine, steroids, others.

Echocardiography at least once during the study period

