Consecutive adult patients (≥ 18 years) with septic shock admitted to the intensive care unit will be considered eligible. Septic shock is defined as suspected or confirmed infection, plus hyperlactatemia (≥ 2.0 mmol per liter) and vasopressor requirements due to refractory hypotension.¹⁰ This latter is characterized as a systolic blood pressure (SBP) < 90 mmHg or a mean arterial pressure (MAP) < 65 mmHg after an intravenous fluid load of at least 20 ml/kg, administered over the course of 60 minutes.

Patients will be excluded in case of:

- pregnancy;
- anticipated surgery or dialysis procedure during the first 8 hours after septic shock diagnosis;
- Do-not-attempt-resuscitation status;
- active bleeding;
- acute hematological malignancy;
- concomitant severe acute respiratory distress syndrome (ARDS);
- more than 4h after the onset of septic shock criteria.

Recruitment

Information that will be included in the CONSORT flow diagram is shown in Fig 2.

Withdrawal/follow-up

We will tabulate the number of patients whose consent for trial participation is withdrawn either by the patient or his or her legal representative. When consent is withdrawn for trial

participation we will nevertheless attempt to obtain consent for collecting and analyzing follow-up data. These cases should also be reported.

Baseline patient characteristics

The baseline characteristics to be registered during the trial will be presented as in mock table 1.

ANALYSIS

Outcome definitions

Our primary outcome is all-cause mortality within 28 days.

Our secondary outcomes are:

- All-cause mortality within 90 days;
- Mechanical ventilation-free days during the first 28 days after randomization. A day free of mechanical ventilation is defined as no need of invasive mechanical ventilation in any time during a given day;
- Renal replacement therapy-free days during the first 28 days after randomization;
- Vasopressor-free days during the first 28 days after randomization;
- Organ dysfunction assessed with the Sepsis-related Organ Failure Assessment (SOFA) score at 72 hours after randomization;¹⁵
- ICU and hospital lengths of stay, truncated at 90 days;

Our tertiary exploratory outcomes are:

- Amount of resuscitation fluids in the first 8 and 24 hours after randomization;
- Total fluid balance in the first 8, 24, 48 and 72 hours;

- Occurrence of intra-abdominal hypertension (IAH) during the first 72 hours after randomization (%).
- Use of RRT (%) within 28 days;

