Lactate, mean, mmol/L	PPTR	x.xx	x.xx	x.xx	x.xx	x.xx	x.xx	x.xx
	LTR	x.xx	x.xx	x.xx	x.xx	x.xx	x.xx	x.xx
	P-value	-	x.xx	x.xx	x.xx	x.xx	x.xx	x.xx
Capillary refill time, median, sec	PPTR	x	x	x	x	x	x	x
	LTR	x	x	x	x	x	x	x
	P-value	-	x.xx	x.xx	x.xx	x.xx	x.xx	x.xx
Central venous oxygen saturation, mean, %	PPTR	xx	-	-	xx	xx	xx	xx
	LTR	xx	-	-	xx	xx	xx	xx
	P-value	-	-	-	x.xx	x.xx	x.xx	x.xx
Delta PaCO ₂ , mean, mmHg	PPTR	xx.x	-	-	xx.x	xx.x	xx.x	xx.x
	LTR	xx.x	-	-	xx.x	xx.x	xx.x	xx.x
	P-value	-	-	-	x.xx	x.xx	x.xx	x.xx
Mottling score, median	PPTR	x	-	-	x	x	x	x
	LTR	x	-	-	x	x	x	x
	P-value	-	-	-	x.xx	x.xx	x.xx	x.xx

Abbreviations: Delta PaCO₂, central venous-arterial pCO₂ gradient

Table 3. Outcomes of Patients Treated with Peripheral Perfusion-Targeted Resuscitation versus Lactate-Targeted Resuscitation

Outcome	Peripheral perfusion-targeted resuscitation (n=xxx)	Lactate-targeted resuscitation (n=xxx)	Type of effect estimate	Effect estimate (95% CI)	P Value
Primary Outcome					
Death within 28 days, no. (n%)	xx (xx.x)	xx (xx.x)	Hazard ratio	x.xx (x.xx to x.xx)	x.xx
Secondary Outcomes					
Death within 90 days, no. (n%)	xx (xx.x)	xx (xx.x)	Hazard ratio	x.xx (x.xx to x.xx)	x.xx
Mechanical ventilation-free days within 28 days, mean (SD)	xx.x	xx.x	Mean difference	x.x (x.x)	x.xx
Renal replacement therapy-free days within 28 days, mean (SD)	xx.x	xx.x	Mean difference	x.x (x.x)	x.xx
Vasopressor-free days within 28 days, mean (SD)	xx.x	xx.x	Mean difference	x.x (x.x)	x.xx
SOFA, mean (SD)					
SOFA at 8h	x.x	x.x	Mean difference	x.x (x.x)	x.xx
SOFA at 24h	x.x	x.x	Mean difference	x.x (x.x)	x.xx
SOFA at 48h	x.x	x.x	Mean difference	x.x (x.x)	x.xx
SOFA at 72h	x.x	x.x	Mean difference	x.x (x.x)	x.xx
ICU length of stay, mean (SD), d	x.x	x.x	Mean difference	x.x (x.x)	x.xx
Hospital length of stay, mean (SD), d	x.x	x.x	Mean difference	x.x (x.x)	x.xx
Tertiary Outcomes					
Amount Resuscitation fluids, mean (SD), mL					
At 8 h	xxxx (xxxx)	xxxx (xxxx)	Mean difference	xxx (xxx to xxx)	x.xx
At 24 h	xxxx (xxxx)	xxxx (xxxx)	Mean difference	xxx (xxx to xxx)	x.xx
Total fluid balance, mean (SD), mL					
At 8 h	xxxx (xxxx)	xxxx (xxxx)	Mean difference	xxx (xxx to xxx)	x.xx
At 24 h	xxxx (xxxx)	xxxx (xxxx)	Mean difference	xxx (xxx to xxx)	x.xx
At 72 h	xxxx (xxxx)	xxxx (xxxx)	Mean difference	xxx (xxx to xxx)	x.xx

Intra-abdominal hypertension, no. (%)	xx (x.x)	xx (x.x)	Risk difference	x.x (x.x to x.x)	x.xx
Use of renal replacement therapy, no. (%)	xx (x.x)	xx (x.x)	Risk difference	x.x (x.x to x.x)	x.xx

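### Intra-abdominal hypertension is tested between arms although pressure was measured only on the suspicion of an unblinded team, so a difference in detection can appear as, or hide, a treatment effect

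*SAP*

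**What the plan says.** The SAP (Outcome definitions) lists "Occurrence of intra-abdominal hypertension (IAH) during the first 72 hours after randomization" under the line "Our tertiary exploratory outcomes are". Directly below the list it states that "The protocol did not call for systematic measurement of intra-abdominal pressure" and that "intra-abdominal pressure was measured according to physicians' discretion when they suspected of intra-abdominal hypertension".

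The SAP's Analysis methods section assigns a risk difference with 95% CI and a Fisher's exact P value to binary secondary and tertiary outcomes other than 90-day mortality and renal replacement therapy. IAH falls in that group. Mock Table 3, intended for the main results paper, has a row "Intra-abdominal hypertension, no" (with percentage) showing a risk difference, CI and P value. Its columns are headed by the arm totals.

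The protocol's Blinding section says that "blinding of the medical team is not feasible". Its Background section hypothesises less fluid, lower positive balances and fewer organ dysfunctions, including gastrointestinal ones, under peripheral perfusion-targeted resuscitation (PPTR) than under lactate-targeted resuscitation (LTR). The SAP's Harms section says the tertiary outcomes, among others, are meant to capture possible harms of the strategies. The SAP's Missing data section deals only with the primary outcome.

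**The concern.** IAH can be recorded only in a patient whose pressure was measured. Under this plan the decision to measure is made after randomisation, on suspicion, by staff who know the arm. The recorded rate therefore combines how often IAH occurs with how often it is looked for. Randomisation balances neither the looking nor the product of the two.

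The trial's own hypothesis gives staff a reason to suspect IAH differently by arm. If a patient is expected to receive less fluid, or visibly does, a physician may be slower to think of abdominal hypertension. That makes arm-dependent detection plausible, although it does not establish it.

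Neither document gives a pressure threshold for IAH, a rule for coding unmeasured patients, a plan to report how many were measured, or a sensitivity analysis for this outcome. A P value produced this way could be cited as evidence on gastrointestinal dysfunction or, given the Harms section, on safety.

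**Working it through.** **The plan's own figure.** The only design calculation in the documents is for mortality: 210 per group, 45% versus 30%, two-sided 5%, approximately 90% power. A two-proportion normal approximation without continuity correction gives 89.1%, so that figure reproduces. No figure is stated for IAH.

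**Inputs from the documents.** 210 per arm; two-sided α of 5%; Fisher's exact test (SAP, Sample size, Confidence intervals and P values, and Analysis methods).

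**Assumptions, because the documents give no values.** The true IAH risk is the same in both arms (no treatment effect). An unmeasured patient is counted as not having IAH. Detection is the probability that a true case is measured and found. This is the relevant quantity because measurement was triggered by suspicion, so true cases were presumably measured more often than other patients.

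**Formula.** Recorded risk in an arm = true risk × detection in that arm. The probability of P ≤ 0.05 is obtained by summing the product of the two binomial distributions (n = 210 each) over all 2×2 tables that the two-sided Fisher test rejects.

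| True risk, both arms | Detected, LTR vs PPTR | Recorded, LTR vs PPTR | Spurious difference | P ≤ 0.05 |
|---|---|---|---|---|
| 20% | 60% vs 60% | 12% vs 12% | 0 points | 3.6% |
| 20% | 30% vs 30% | 6% vs 6% | 0 points | 3.1% |
| 10% | 60% vs 50% | 6% vs 5% | 1 point | 4.7% |
| 10% | 90% vs 80% | 9% vs 8% | 1 point | 4.5% |
| 20% | 90% vs 80% | 18% vs 16% | 2 points | 6.6% |
| 30% | 90% vs 80% | 27% vs 24% | 3 points | 9.0% |
| 20% | 60% vs 40% | 12% vs 8% | 4 points | 22.7% |
| 30% | 60% vs 30% | 18% vs 9% | 9 points | 73.7% |

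Fisher's test is conservative, so the reference rate with equal detection is about 3–4% rather than 5%. The lower detection is placed in PPTR only for illustration. With equal arm sizes, reversing the arms changes the sign and leaves the probabilities unchanged.

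**The opposite error.** Suppose the true risk is 20% in PPTR and 30% in LTR, with 60% and 40% of cases detected. Recorded risks are 0.20 × 0.60 = 12% and 0.30 × 0.40 = 12%. A real 10-point difference vanishes. With complete detection in both arms, Fisher's test would find it in 62% of trials.

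**Consistency of the two documents.** The protocol's Baseline data list includes "intraabdominal pressure (IAP), NE levels, diuresis" among the haemodynamic variables, and its Evolution list has haemodynamics recorded hourly to 8 hours without saying whether pressure is included. This sits uneasily with the SAP's statement that systematic measurement was not called for. Even if pressure was collected hourly to 8 hours, no routine pressure measurement is listed from 8 to 72 hours.

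**The case against.** The outcome is tertiary and labelled exploratory, the SAP discloses the measurement limitation beside the outcome list, and no conclusion on mortality depends on it. All of that is true and limits the severity. But the exploratory label invites caution about the strength of evidence and does not remove bias in ascertainment. The disclosure left the planned analysis unchanged, and the mock table carries no footnote.

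A stronger objection is that the larger figures rest on detection gaps of 20 or 30 points that nothing in the documents supports. Because measurement followed suspicion, detection among true cases may have been high in both arms. At 90% versus 80% the false-positive rate is only 5–9%, and at the lowest settings there is no excess over the nominal 5%. This stands: the calculation shows what can happen, not what did.

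Two stronger readings are tempting. A reader might infer that the bias favours PPTR. The documents state a hypothesis about fluid, but nothing shows that suspicion or measurement differed by arm; and if fluid exposure does differ, lower suspicion may partly track lower true risk. A reader might also infer that unmeasured patients are counted as free of IAH. A count and percentage under the arm totals, together with the intention-to-treat rule, suggest this, but that rule says only that patients are analysed as randomised. The coding and the denominator are unspecified.

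**Conclusion.** The concern holds as a weakness of the planned analysis. Detection depends on the suspicion of staff who know the arm, the handling of unmeasured patients is not stated, and a formal between-arm comparison is planned regardless. A detection difference can therefore produce or mask an apparent effect on IAH.

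Size and direction are unknown. With equal true risk and unmeasured patients counted as negative, the chance of P ≤ 0.05 runs from about 5% to about 74% over the assumed range, with 23% for the central illustration. The documents support no particular point in that range. The primary result is unaffected. Severity is minor to moderate: the outcome is tertiary, but it also serves as harms information and the correction is cheap.

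**What to change.** In the SAP's Analysis methods section and mock Table 3:

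- Remove the between-arm risk difference, CI and P value for IAH.
- Report by arm the number randomised, the number with pressure measured after randomisation, and the number with IAH detected. Label the row 'clinically detected IAH, descriptive only'.
- State the definition of IAH, and state that unmeasured patients have unknown status rather than being negative.
- Add a note that rates among measured patients are not a randomised comparison, because being measured is itself a post-randomisation event. Restricting a test to measured patients would not solve the problem.

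Separately, reconcile the protocol's baseline listing of intra-abdominal pressure with the SAP's statement on systematic measurement, and say at which times pressure was recorded.

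The cost is a change of wording and the loss of one tertiary effect estimate with its P value. No new measurements are proposed. The by-arm count of patients measured does depend on post-randomisation pressures having been recorded, which the protocol's data list does not make explicit.

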Interim analyses were conducted after the inclusion of the first 100 patients and at 75% of the sample size (300 patients). Only the independent data and safety monitoring committee (DSMC) had access to results of those analyses. The DSMC is comprised by 5 experienced intensivists and trialists, and 1 senior statistician. The DSMC established no *a priori* statistical stopping guidance according to efficacy, safety or futility. The DSMC recommended that the trial should continue without alterations after those analyses.

TIMING OF FINAL ANALYSIS

All outcomes will be analyzed simultaneously after we have completed the 90-day follow-up of all patients and the database has been locked.

TIMING OF OUTCOME ASSESSMENTS

We will assess outcomes at 8, 24, 48, and 72 hours; at hospital discharge; and at 28 and 90 days,

STATISTICAL PRINCIPLES

Confidence intervals and P values

We will present 95% confidence intervals for effect estimates on all primary and secondary outcomes. All hypothesis test will be two-sided with an α of 5%. We will not adjust P-values and confidence intervals for analyses of primary or secondary outcomes. Therefore, all results for secondary outcomes should be interpreted as exploratory.

Adherence and protocol deviations

We will report the numbers and percentages of non-adherence to randomly allocated treatment.

Protocol deviations will be assessed and registered by the local coordinators at each center. Major deviations are defined as wrong inclusion (misjudgment of inclusion or exclusion criteria) or inadequate resuscitation procedures during the study period.

Analysis populations

All analyses will be conducted according to the intention-to-treat principle. Thus, patients will be analyzed in the groups that they were randomly assigned.

TRIAL POPULATION

Screening data

An active daily screening for potentially eligible patients will be performed at all the participating ICUs. Screened patients include all patients admitted to the participating ICUs with septic shock criteria or who develop these criteria during their ICU stay.¹⁰ Patients will be either included or excluded for the study, and the reasons for these latter registered and communicated to the SSC on a weekly basis.

Eligibility

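### 90-day mortality is the only Cox mortality model in the SAP without the five baseline covariates, and mock Table 3 does not label the difference: a cheap improvement, likely but not certain to add power

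*SAP*

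**What the plan says.** Under Analysis methods, the SAP fits the 28-day Cox model "with adjustment for 5 pre-specified baseline covariates: APACHE II score, SOFA score, lactate level, CRT and source of infection, as fixed" effects. The Subgroup analyses section uses the same covariate set for its interaction models. The Sensitivity analysis section specifies a site-frailty model with "adjustment for the same baseline co-variables as in the main analysis". For death by day 90, and for renal replacement therapy (RRT) by day 28, the effect "will be assessed with Cox-proportional hazard model without adjustment for baseline covariates". No reason is given.

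Mock Table 3 gives the 28-day and 90-day death rows the same effect type, *Hazard ratio*, with nothing to show that one is adjusted and the other is not. No unadjusted 28-day or adjusted 90-day hazard ratio is planned.

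Three other statements bear on the point:

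- Under Confidence intervals and P values: "all results for secondary outcomes should be interpreted as exploratory".
- Under Analysis populations: "All analyses will be conducted according to the intention-to-treat principle".
- Under Missing data, multiple imputation applies only "if there are cases without no follow-up information at all". No rule is given for a patient who has follow-up but lacks a baseline covariate.

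**The concern.** Death by day 90 is the primary event followed for longer, and the covariates are already required for the primary model. Leaving them out has two consequences.

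The first is power. If the covariates predict death, the adjusted Cox test has a better chance of detecting a real effect at no cost in data.

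The second is comparability. The Cox hazard ratio is non-collapsible: leaving out prognostic covariates moves it towards 1 even under perfect randomisation. An adjusted 28-day value beside an unadjusted 90-day value can therefore look like a fading effect when nothing has faded, and the planned tables give the reader no matched pair to check this against.

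**Working it through.** **1. The plan's own figure.** Inputs from the SAP, Sample size: 210 per group, mortality 45% against 30%, two-sided alpha 5%.

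- HR = ln(0.70)/ln(0.55) = 0.597. Expected deaths = 210 × (0.45 + 0.30) = 157.5.
- Power = Φ(|ln HR| × √(deaths/4) − 1.96) = Φ(0.517 × 6.27 − 1.96) = 90.0%. The two-proportion formula gives 89.1%. The stated figure of about 90% is reproduced.
- For 45% against 35%, the same formulas give 56.5% and 55.3%, against the protocol's 57%.

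**2. Unadjusted 90-day power.** The documents give no 90-day rates. Assume 52% against 42%.

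- HR = ln(0.58)/ln(0.48) = 0.742. Deaths = 210 × 0.94 = 197.4.
- Power = Φ(0.298 × 7.03 − 1.96) ≈ 55%.

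**3. Adjusted 90-day power, by simulation.** There were 5,000 trials per scenario (Monte Carlo error about 0.7 points near 55%). Each had 420 patients in blocks of eight, Weibull times set to 45% lactate-arm mortality at day 28 and 50% or 52% at day 90, and a constant treatment hazard ratio. The adjusted model used four continuous covariates plus five dummies for the six infection sources in mock Table 1. Strength is the assumed SD of the prognostic score on the log-hazard scale; one SD multiplies the hazard by 1, 1.35, 1.65, 2.2 or 2.7. Changes are taken before rounding.

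| Score SD | 0 | 0.3 | 0.5 | 0.8 | 1.0 |
|---|---|---|---|---|---|
| 52% v 42%, unadjusted power (%) | 55 | 56 | 57 | 56 | 56 |
| 52% v 42%, adjusted power (%) | 55 | 58 | 63 | 70 | 78 |
| Change (points) | −1 | +2 | +6 | +14 | +21 |
| 50% v 40%, change | 0 | +1 | +5 | +13 | +21 |
| 52% v 37%, change | 0 | +1 | +4 | +7 | +9 |
| 52% v 42%, covariates uninformative after day 28, change | – | +1 | +5 | +11 | +16 |

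Type I error was 4.8–5.3% unadjusted and 4.6–5.5% adjusted. A separately coded simulation (1,500 trials per cell, 50% against 40%) gave adjusted power of 53, 58, 60, 71 and 76%, against 53, 57, 56, 57 and 56% unadjusted.

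**4. Where the gain comes from.** In that second simulation at SD 0.8, the unadjusted HR was 0.732 (SE of the log HR 0.147) and the adjusted HR 0.687 (SE 0.150).

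- Unadjusted: 0.312/0.147 = 2.12, and Φ(2.12 − 1.96) ≈ 56%.
- Adjusted: 0.375/0.150 = 2.50, and Φ(2.50 − 1.96) ≈ 71%.

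The standard error does not shrink. The estimate moves further from 1.

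**5. Missing covariates.** One continuous covariate was missing completely at random, at 52% against 42%. Changes are against the unadjusted model on all 420 patients.

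| Score SD | 0 | 0.3 | 0.5 | 0.8 | 1.0 |
|---|---|---|---|---|---|
| 10% missing, patients dropped | −4 | −3 | +1 | +9 | +16 |
| 10% missing, mean imputed | −1 | +3 | +6 | +13 | +20 |
| 15% missing, patients dropped | −6 | −4 | −1 | +6 | +14 |
| 15% missing, mean imputed | −1 | +2 | +6 | +13 | +20 |

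**6. Comparability when the effect does not fade (SD 0.3–1.0).**

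| | Plan as written | Both models adjusted |
|---|---|---|
| 90-day HR higher than 28-day HR | 57–86% of trials | 48–51% |
| 28-day significant, 90-day not; 10-point effect | 5–21% | 2–3% |
| 28-day significant, 90-day not; 15-point effect | 2–9% | 0.2–1.3% |

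Under the plan, the median gap between the two hazard ratios is 0.01–0.08.

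**7. Is useful covariate strength plausible?** The SAP cites mortality under 10% with a normal CRT and above 40% with abnormal perfusion. Take 10% with a normal CRT, 45% overall and, as assumptions, 46%, 50% or 60% with an abnormal CRT. The share with a normal CRT is then w = 0.01/0.36, 0.05/0.40 or 0.15/0.50. The SD from CRT alone is ln[ln(1 − p)/ln(0.90)] × √(w(1 − w)), with p the abnormal-CRT mortality: about 0.3, 0.6 or 1.0. The cited rates come from different cohorts, so this shows plausibility and is not an estimate.

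**The case against.** Read by outcome tier, the SAP is nearly consistent. The primary outcome gets the five covariates, and no secondary or tertiary outcome does. In-hospital mortality and length of stay are also unadjusted, and the protocol had planned chi-squared tests with risk ratios for binary secondary outcomes. This explains the choice, though the tier rule is not absolute, since 72-hour SOFA is adjusted for its baseline. In-hospital mortality uses a risk difference and Fisher's test, so the 90-day model remains the only unadjusted Cox mortality model.

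No decision depends on the 90-day p-value, and secondary results are exploratory. That stands, and it limits the consequence.

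Adjustment does not narrow the interval; it changes the target from a marginal to a conditional hazard ratio. The marginal one matches the Kaplan–Meier curves and the death percentages. That also stands, and is the reason to keep unadjusted values in the report.

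The 0.01–0.08 gap is small beside the uncertainty: a hazard ratio of 0.74 with SE 0.144 has an interval of about 0.56–0.98. Death counts and curves are shown, and the methods text discloses the difference. These points reduce the risk of misreading without supplying a matched pair.

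Missingness of 10–15% is an assumption and may be too high. Lactate is an eligibility criterion, the other covariates are listed baseline data, and the protocol plans weekly missing-data checks. The missing-covariate gap also affects the primary model, so the rule is needed in any case.

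**Conclusion.** The point holds as a worthwhile, low-cost improvement. The planned 90-day analysis is valid and is not an error.

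For a 10-point difference, adjustment probably adds power: nil to 2 points with weak covariates, about 5 or 6 at SD 0.5, 13 or 14 at SD 0.8 and 21 at SD 1.0. The sign is not guaranteed. The gain is nil if the covariates are not prognostic, and becomes a loss of 3 to 6 points if they are weak and 10–15% of patients are dropped. These sizes rest on assumed 90-day rates, an assumed covariate strength and proportional hazards. The imputation result was tested only for one covariate missing completely at random and replaced by its mean.

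The labelling and comparability point does not depend on how large the gain is. Confidence is medium overall.

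**What to change.** Replace the 90-day part of the sentence under Analysis methods with wording such as:

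> Death by day 90 will be analysed with the Cox model of the primary analysis, including its five baseline covariates. Missing baseline covariates will be imputed by the same named method in both models, so that no randomised patient with follow-up is dropped. Unadjusted hazard ratios at 28 and 90 days will be reported as supportive. Table 3 will mark each hazard ratio as adjusted or unadjusted.

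The RRT model may stay as planned: it concerns a tertiary outcome and a different event.

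If the sponsor prefers the marginal hazard ratio as the main 90-day result, the minimum is to keep it, add the labels, and report an unadjusted 28-day and an adjusted 90-day hazard ratio beside it.

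The cost is a few SAP sentences and a table label before database lock, with no new data and the same covariates and code as the primary model. The downside is a little more analysis work and the need for a shared missing-covariate rule. Without that rule, the gain can vanish or become a small loss.
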